### Appendix B Criteria for Markedly Abnormal Values for Vital Signs

Parameter	Unit	Lower Criteria	Upper Criteria
Pulse	bpm	<50	>120
Systolic blood pressure	mm Hg	<85	>180
Diastolic blood pressure	mm Hg	<50	>110
Body temperature	°C	<35.6	>37.7

### Criteria for Identification of Markedly Abnormal Orthostatic Changes

Parameter	Criteria
Orthostatic Hypotension	(Orthostatic Systolic Blood Pressure <-20 mm Hg OR Orthostatic Diastolic Blood Pressure <-10 mm Hg) AND Heart Rate Increase >20 beats/min

[figure not shown]
Note: Orthostatic measurement = standing vital measurement – supine vital measurement.

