The second study (TAK-831-1003) used positron emission tomography (PET) to investigate brain DAO enzyme occupancy by TAK-831 after a single oral dose (100 to 500 mg) in healthy male subjects. The results demonstrated that the tracer crossed the blood brain barrier in humans with highest uptake in the cerebellum and brainstem and low uptake in the frontal cortex, a distribution consistent with DAO distribution in rodents [15]. Administration of TAK-831 blocked uptake of the tracer indicating that the TAK-831 binding to brain DAO is specific. Using a multilinear analysis-1 model [16], the in vivo TAK-831 plasma concentration at 50% occupancy (EC₅₀) for brain DAO was estimated to be 12.7 ng/mL (95% CI=2.3, 23.1). In conclusion, this study demonstrates that TAK-831 accesses the DAO enzyme in the brain and displays high target occupancy at tested doses that have been shown to be safe in Study TAK-831-1001.

In both phase 1 studies (TAK-831-1001, TAK-831-1003), TAK-831 was generally safe and well tolerated at the doses administered in healthy subjects. No deaths, serious adverse events (SAEs), or treatment-emergent adverse events (TEAEs) leading to discontinuation were reported in either study. The most frequently reported TEAEs in Study TAK-831-1001 were postural dizziness and headache. The rate of postural dizziness in subjects receiving TAK-831 did not markedly differ from the rate observed in subjects receiving placebo. In Study TAK-831-1003 (PET occupancy, single dose), the most common TEAEs overall were related to the catheter site (pain, bruise, or hematoma); the remaining TEAEs were consistent with those reported in Study TAK-831-1001. No concerning trends in clinical laboratory, electrocardiogram (ECG), or vital sign data were observed in either study.

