9.1.5 Vital Sign Procedure

Vital signs will include oral body temperature, respiratory rate, blood pressure, and heart rate (beats per minute). Blood pressure and heart rate will be measured in 2 positions: after 5 minutes supine and then after 1 and 3 minutes standing.

Vital signs should be measured at the same time of the day across visits, if possible. When vital signs are scheduled at the same time as blood draws, the blood draw will take priority and vital signs will be obtained within 0.5 hours before or after the scheduled blood draw.

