### 5.3 Exploratory Endpoints

The following additional safety endpoints:

- Percentage of subjects who meet the markedly abnormal criteria for clinical laboratory tests at least once post dose.
- Percentage of subjects who meet the markedly abnormal criteria for vital sign measurements at least once post dose.
- Percentage of subjects who meet the markedly abnormal criteria for 12-lead ECG parameters at least once post dose.

The following PK parameters for TAK-831 for each regimen:

- $t_{max}$ .
- $t_{1/2z}$ .
- $CL/F$ .
- $V_z/F$ .

CCI

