### 7.12.3 Vital Signs

Vital sign measurements include body temperature, respiratory rate, blood pressure, and heart rate (beats per minute). Vital signs are measured at Screening, Check-in Period 1, Day 1 (within 50 minutes before dosing and at 1, 4, and 12 hours post dose), 2, 3, 4 and 6 of each period, Check-in Period 2 (also Day 8 of Period 1) and at Study Exit (Day 8 of Period 2 or Early Termination).

Descriptive statistics (N, mean, median, SD, minimum and maximum) of vital signs in each position (supine, standing and orthostatic change for blood pressure and heart rate) will be summarized for baseline, post dose, and change from baseline to post dose by regimen. The Baseline for each regimen is defined as the last observation prior to the dose of study drug in the corresponding period. Only the scheduled measurements will be included in the summary. No statistical tests will be performed.

All individual vital signs that meet Takeda's predefined criteria for MAVs ([Appendix B](#)) will be listed. The number and percentage of subjects with at least 1 post dose markedly abnormal vital sign measurement will be summarized by regimen. Subjects who meet the MAV criteria will be mapped to their respective qualifying vital sign result. All post dose MAV vital signs, including both scheduled and unscheduled measurements, will be included in the MAV summaries.

All clinical laboratory data will be presented in both SI and conventional units in data listings.

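### The SAP counts a postural blood-pressure fall as orthostatic hypotension only if heart rate also rises by more than 20 beats/min, so the number of subjects with a fall alone is never tabulated

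*SAP*

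**What the plan says.** SAP Appendix B, under the criteria for markedly abnormal orthostatic changes, shows one row, labelled orthostatic hypotension. Its condition is a systolic change below -20 mm Hg or "Orthostatic Diastolic Blood Pressure <-10 mm Hg) AND Heart Rate Increase >20 beats/min", with the systolic and diastolic terms bracketed together. The note beneath gives the direction of the difference: "Orthostatic measurement = standing vital measurement – supine vital measurement".

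SAP 7.12.3 applies Appendix B to the vital-sign data: "The number and percentage of subjects with at least 1 post dose markedly abnormal vital sign measurement will be summarized by regimen". That count supplies the exploratory safety endpoint in SAP 5.3: "Percentage of subjects who meet the markedly abnormal criteria for vital sign measurements at least once post dose".

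Appendix B also sets absolute limits (systolic <85 or >180, diastolic <50 or >110 mm Hg, pulse <50 or >120 bpm) without saying which position they apply to. SAP 7.12.3 further provides that "vital signs in each position (supine, standing and orthostatic change for blood pressure and heart rate) will be summarized for baseline, post dose", using N, mean, median, SD, minimum and maximum by regimen. SAP 7.1 puts all raw and derived data in listings.

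Protocol 9.1.5 takes blood pressure and heart rate "after 5 minutes supine and then after 1 and 3 minutes standing". Appendix B does not say which standing reading is used, or whether the fall and the heart-rate rise must come from the same one.

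**The concern.** Because of the AND, the size of the blood-pressure fall alone never makes a subject a case. A 21 mm Hg systolic fall with a rise of 21 beats/min is counted; a much larger fall with a rise of 20 is not. A regimen table showing no orthostatic hypotension would then be compatible with several subjects having had marked falls.

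The count has some relevance here. Safety and tolerability in the fed and fasted states is the secondary objective, food is expected to raise exposure, and Protocol 4.1 reports: "The most frequently reported TEAEs in Study TAK-831-1001 were postural dizziness and headache". A by-regimen count of postural falls is the natural objective companion to any postural-dizziness events. At stake is whether that table can be read as the number of subjects whose pressure fell.

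**Working it through.** The plan states no figure on this point, so there is none to reproduce. The check applies the rule literally and then illustrates its effect under stated assumptions.

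**1. The rule applied to example readings** (supine to standing, with heart rate, HR)

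| Supine | Standing | Change | BP condition met | Counted as orthostatic hypotension | Absolute limit met |
|---|---|---|---|---|---|
| 120/75, HR 60 | 90/60, HR 70 | -30/-15, HR +10 | yes | no | no |
| 140/90, HR 60 | 85/50, HR 80 | -55/-40, HR +20 | yes | no (+20 is not >20) | no (85 is not <85; 50 is not <50) |
| 120/75, HR 60 | 90/60, HR 81 | -30/-15, HR +21 | yes | yes | no |
| 120/75, HR 60 | 80/48, HR 70 | -40/-27, HR +10 | yes | no | yes, if the limits cover standing readings |

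The second row starts from the upper supine limits for entry (Protocol 7.2, criterion 21: 90 to 140 systolic, 50 to 90 diastolic).

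**2. What the absolute limits leave open.** Suppose they do cover standing readings. In whole mm Hg, a qualifying systolic fall f from supine S escapes the limit when f ≥ 21 and S - f ≥ 85, that is, when f lies between 21 and S - 85.
- S = 140: falls of 21 to 55 escape.
- S = 120: falls of 21 to 35 escape.
- S = 105 or lower: none escapes, since 105 - 21 = 84.

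For diastolic falls from supine D the range is 11 to D - 50.
- D = 90: 11 to 40.
- D = 75: 11 to 25.
- D = 60 or lower: none, since 60 - 11 = 49.

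The limits therefore close part of the gap, mainly for subjects with low supine pressure.

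**3. Share of falls that fail the heart-rate condition (assumed inputs).** The documents give no distribution of orthostatic change. Assume the systolic change is normal with mean -2 and SD 10, and the heart-rate change is normal with mean m and SD s, with correlation r. With a = (-20 + 2)/10 = -1.8 and b = (20 - m)/s,

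P(HR rise >20 given systolic change <-20) = [Φ(a) - Φ₂(a, b; r)] / Φ(a),

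where Φ₂ is the bivariate normal distribution function.

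| m, s | r = 0 | r = -0.3 | r = -0.5 |
|---|---|---|---|
| 8, 8 | 0.07 | 0.19 | 0.32 |
| 12, 8 | 0.16 | 0.36 | 0.54 |
| 15, 10 | 0.31 | 0.57 | 0.75 |

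A simulation of 2,000,000 draws agrees to within 0.01. The share that fails the heart-rate condition runs from 1 - 0.75 = 25% to 1 - 0.07 = 93%. This is per reading and uses the systolic condition only.

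**4. Effect on the number of subjects (assumed inputs).** All 16 subjects are to receive each regimen. Let p be the share with a qualifying fall and q the share of those who also meet the heart-rate condition. The expected counts are 16p on blood pressure alone and 16pq under the SAP rule. The chance of counting at least one subject is 1 - (1 - p)^16 and 1 - (1 - pq)^16 respectively.

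For p = 0.20, the blood-pressure condition alone gives 3.2 subjects and a chance of 0.97. The SAP rule gives:
- q = 0.10: 0.3 subjects, chance 0.28
- q = 0.25: 0.8 subjects, chance 0.56
- q = 0.50: 1.6 subjects, chance 0.82
- q = 0.75: 2.4 subjects, chance 0.93

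Over p = 0.10 to 0.30 and q = 0.10 to 0.75, the expected count is 1.6 to 4.8 on blood pressure alone and 0.16 to 3.6 under the SAP rule.

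**The case against.** The strongest reply is that nothing is hidden. The minimum orthostatic change by regimen would show the single worst fall, the listings hold every reading, and with 16 subjects anyone can count falls by hand. Symptomatic falls reported as adverse events enter the TEAE tables. This largely stands: what is missing is a prespecified tabulated count, not the data.

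Second, these are the sponsor's predefined screening criteria for marked abnormality. No passage contradicts them, and the documents contain no standard against which the combined definition could be called wrong. That stands too, so this point does not say which definition is right.

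Third, a reader might infer from the frequency of postural dizziness that the drug has a known postural effect. The documents do not support this. Protocol 4.1 adds that the rate did not differ markedly from placebo and that vital signs showed no concerning trends in either earlier study.

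Fourth, a reader might infer that an exposure doubling is expected here. The roughly 2-fold increase in Protocol 4.1 came from a 100 mg T1 tablet with a high-fat meal. For T2 with Ensure Plus, Protocol 6.2 expects an increase and makes its size the question; the ratio of 2 in Protocol 13.3 is a planning assumption. Protocol 6.2 also expects exposures within the range already observed.

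Finally, the heading of the orthostatic table is plural, only one row is visible, and a figure beside it is not shown in the text available. Another row or note cannot be excluded.

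**Conclusion.** The point holds as a limited reporting gap. On the visible text, a postural fall of any size without a heart-rate rise above 20 beats/min is not counted as orthostatic hypotension, and the absolute limits pick up only some of these falls. No planned table gives the number of subjects with a blood-pressure fall alone.

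Its size cannot be derived from the documents. The 25% to 93% range rests wholly on assumed means, SDs and correlations. A reader might infer that most positive readings are filtered out, but three of the nine assumed scenarios (0.54, 0.57, 0.75) keep most of them. The example from 140/90 likewise shows what the rule permits, not what is typical.

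The consequence is confined to one component of an exploratory safety endpoint with no statistical testing. The primary PK analysis and the sample size are unaffected. It is worth changing because the change is cheap.

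**What to change.** In SAP Appendix B and 7.12.3, add a by-regimen line giving the number and percentage of subjects who meet the existing blood-pressure condition alone (systolic change <-20 or diastolic change <-10 mm Hg) at the 1- or 3-minute standing reading at least once post dose. Keep the combined criterion as its own line, and state which standing reading it uses and whether the fall and the heart-rate rise must come from the same one. State also whether the absolute limits apply to supine readings, standing readings or both. If the part of Appendix B not visible here already contains a blood-pressure-only row, only these clarifications are needed.

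The cost is one line in an existing table, from data already collected. The downside is more flagged readings, some of them ordinary variation; keeping the combined line beside the new one lets a reader tell the two apart.

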### Appendix C Criteria for Markedly Abnormal Values for Electrocardiograms

Parameter	Lower Criteria	Upper Criteria
Heart rate	<50 beats per minute	>120 beats per minute
PR	≤80 milliseconds	≥200 milliseconds
QTcB Interval	≤300 milliseconds	≥500 milliseconds OR ≥30 milliseconds change from baseline and ≥450 milliseconds
QTcF Interval	≤300 milliseconds	≥500 milliseconds OR ≥30 milliseconds change from baseline and ≥450 milliseconds
QRS	≤80 milliseconds	≥180 milliseconds

TAK-831-1004 Statistical Analysis Plan

ELECTRONIC SIGNATURES

Signed by	Meaning of Signature	Server Date (dd-MMM-yyyy HH:mm 'UTC')
PPD 	Biostatistics Approval	09-Jun-2017 20:16 UTC
	Clinical Approval	09-Jun-2017 22:54 UTC
	Clinical Pharmacology Approval	09-Jun-2017 23:23 UTC
	Clinical VP Approval	09-Jun-2017 23:36 UTC
	Pharmacovigilance Approval	12-Jun-2017 19:48 UTC
